Hypothesis 1b: Improvements in language achieved with combined tDCS-behavioral therapy but not behavioral therapy alone will persist at 2 weeks, 2 months and 6 months post-intervention. Hypothesis 1c: Stimulation of the propose areas during behavioral therapy will improve performance in other language and cognitive functions specific to the region of interest. Specifically, for SMG, improvements will be observed in spelling, naming, working memory and repetition; and for IFG and MTG, in spelling, naming, working memory, articulation, and syntactic comprehension. Hypothesis 1d: The therapeutic effect of tDCS will exhibit an interaction between hemisphere of stimulation (left vs. right) and stage of disease (early vs. middle), such that left hemisphere stimulation will be more effective at an early stage, whereas at later stages right hemisphere stimulation. Hypothesis 1e. Improvements in language achieved with combined IFG tDCS-behavioral therapy or sham and behavioral therapy alone will correlate with increases in daily physical activity and evening sleep efficiency and quality (using both self-report and objective measures) and there will be greater improvements in sleep efficiency and exercise in the tDCS condition as opposed to sham, because the area we target (left or right IFG) with 2x2 in electrodes incorporates premotor and motor areas that have

been found to improve the perceived difficulty and amount of exercise and sleep efficiency.

Hypothesis 1f: Beginning with a 3-week CBT treatment with tDCS over the DLPFC before beginning computerized cognitive/speech therapy at home will foster motivation and engagement in the consequent therapy by establishing routine, form, and helping manage psychological barriers to therapy beforehand.

**Primary Objective 2 (imaging):** To develop biomarkers for the effects of intervention using H-MRS. We will use H-MRS to detect NAA and GABA before, after and at follow-up intervals and evaluate the correlation between: (1) NAA/ GABA levels and (2) spelling, naming, and/or repetition accuracy of participants with PPA and MCI at each time point.

Hypothesis 2a: We hypothesize that tDCS coupled with behavioral therapy will result in enhanced, relative to behavioral therapy alone (with sham tDCS), levels of NAA at the stimulation sites where tDCS resulted in improved spelling relative to behavioral therapy alone.

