Hypothesis 2b: We hypothesize that tDCS coupled with spelling therapy will result in reduced, relative to behavioral therapy alone (with sham tDCS), levels of GABA at the stimulation sites where tDCS resulted in improved language relative to behavioral therapy alone.

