We further hypothesize that improvements related to tDCS or sham combined therapy may extend to increases in quality of life as measured by lifestyle activity. Research conducted by [name] lab ([name]) using wearable accelerometers in community-dwelling older adults has demonstrated that low-intensity walking activity related to functional activities of daily living (shopping, vacuuming), were positively associated with several measures of health (self-report and performance-based measures of physical function, quality of life, depressive symptoms) independent of exercise activity (Varma et al., 2013). Low-intensity walking activity is associated with better health. Furthermore, greater daily walking activity was cross-sectionally associated with larger hippocampal volume, an important brain biomarker of memory and risk for dementia (Varma et al., 2015). We hypothesized that the language and other cognitive improvements related to intervention itself (either sham or tDCS) and especially language therapy may further correlate to increases in functional and social activities (e.g. walking to catch a bus, caretaking of grandchildren, and religious activities).

The imaging goal of this study is to develop molecular biomarkers for the effects of intervention using H-MRS. Our aim is to investigate the molecular and cellular mechanisms of tDCS combined with spelling therapy in PPA. In a previous study using spectroscopy, individuals with PPA were found to have a specific neuropeptide signature different from other dementias and healthy controls (Catani et al., 2003), i.e. they had low levels of NAA. In the present study we intend to investigate the modulation of certain

neuropeptides (NAA and GABA) from tDCS. Thus, application of tDCS is expected to increase the levels of NAA and NAA/Cre associated with better performance. Furthermore tDCS is expected to decrease the levels of GABA since anodal tDCS supposedly suppresses the inhibitory system suggesting a locally reduced activity of the GABA-ergic system (Stagg et al., 2011). In the present study we will investigate how tDCS combined with spelling interventions may change the NAA and GABA neurotransmitters' levels.

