
#### Spectroscopy methods:

MRSI will be performed using standard techniques on a 3T Achieva (Philips Healthcare Inc.) system equipped with a 32-channel head coil (InVivo). Metabolite concentrations will be measured from selected brain regions. The scanner will be operating within FDA allowed guidelines for RF power deposition, dB/dt, and acoustic noise at all times. The whole scanning session including acquisition of structural data as well as all spectroscopy sequences of interest will last about 1 hour. Scanning sessions will be performed at the beginning of enrollment, before and after each 5-day (or 15-day) tDCS treatment and at follow-up intervals for up to 8 sessions per participant over a period of 1.5 years. Spectroscopy data will be analyzed by members of the study-team from the Departments of Radiology and Biostatistics using standard procedures.

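### Primary Objective 2 seeks a biomarker of the intervention's effect, but its person-level analysis correlates metabolite levels with accuracy levels and so cannot separate response to tDCS from disease severity

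*Combined protocol and SAP*

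**What the plan says.** Under Objectives, Primary Objective 2 has this purpose: "To develop biomarkers for the effects of intervention using" proton spectroscopy. Its person-level analysis is a correlation of two quantities: "1) NAA/ GABA levels and (2) spelling, naming, and/or repetition accuracy of participants with PPA and MCI at each time point". The analysis is therefore of levels against levels, repeated at each visit. Because the plan is to "detect NAA and GABA before, after and at follow-up intervals", the visits include one before treatment.

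Two hypotheses follow. Hypothesis 2a concerns NAA: "tDCS coupled with behavioral therapy will result in enhanced, relative to behavioral therapy alone (with sham tDCS"). Hypothesis 2b concerns the other metabolite: "tDCS coupled with spelling therapy will result in reduced, relative to behavioral therapy alone (with sham tDCS), levels of GABA". Each is limited to the stimulation sites where tDCS gave better spelling (2a) or language (2b) than behavioural therapy alone.

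The Background section says of an earlier spectroscopy study that "individuals with PPA were found to have a specific neuropeptide signature different from other dementias and healthy controls". It describes that signature in one short phrase: "they had low levels of NAA". For GABA it gives only an expected fall under anodal tDCS.

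Scans are planned at the start of enrolment and then "before and after each 5-day (or 15-day) tDCS treatment and at follow-up intervals" (section 3a, Spectroscopy methods). That section names the departments that will analyse the data but no model. Section 6c contains no spectroscopy analysis; its regression on age and atrophy asks whether tDCS effects vary between participants and does not adjust this correlation. Section 7a describes MRS as an optional part for a subset whose size is not given.

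**The concern.** A biomarker of an intervention's effect has to show that people whose metabolite moves more under the intervention also improve more because of it. A correlation of levels at one visit compares people with each other and does not use the before-and-after pairing. Section 4 admits several PPA variants and MCI, and Hypothesis 1d distinguishes early from middle stage. If participants with more advanced disease have both lower NAA and lower accuracy, the two levels correlate at every visit, under tDCS, under sham, or with no treatment.

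At stake is the reading of a result labelled a primary objective. A significant correlation after treatment could be reported as an intervention biomarker when it reflects only who was more impaired. The protocol uses a better form elsewhere: the Part 2 hypotheses of Primary Objective 3 correlate changes in connectivity with changes in BDNF, and changes in BDNF with changes in therapy outcome.

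**Working it through.** **The plan's own figure.** None is given for the imaging correlation. The only calculated figure is 75% power in section 6c, for the behavioural comparison. It reproduces: 30 × 1.5 = 45 equivalent independent participants, 22.5 per arm, effect size 0.8, two-sided 5% (assumed, since no level is stated) gives 76.5% by the normal formula and 74.6% by the t test. It does not bear on this point.

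**Inputs.** Taken from the documents: 30 participants (section 6c), an optional MRS subset of unstated size (section 7a), levels analysed at each visit, and scans before and after each block. Assumed: an MRS subset of 15 as a smaller case, a two-sided 5% Pearson test, and the share λ of the variance of each measure that is due to stable severity.

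**Model with no tDCS effect.** At every visit, metabolite = √λ·severity + √(1−λ)·noise, and accuracy likewise with independent noise. The expected level correlation is √λ × √λ = λ.

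**Chance of a significant level correlation at one visit (simulation):**

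| Severity share λ | Mean r (n = 30) | Significant, n = 30 | Significant, n = 15 |
|---|---|---|---|
| 10% | 0.10 | 8% | 6% |
| 20% | 0.20 | 19% | 11% |
| 30% | 0.30 | 37% | 19% |
| 50% | 0.49 | 83% | 50% |
| 70% | 0.69 | over 99% | 88% |

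**Hand check at λ = 30%, n = 30 (Fisher's z).** atanh(0.30) × √27 = 0.3095 × 5.196 = 1.61. The chance of exceeding 1.96 is 1 − Φ(1.96 − 1.61) = 1 − Φ(0.35), about 36%, in line with the simulated 37%.

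**A second set-up.** Here part of the remaining variance is also stable within a person. The level correlation at n = 30 is significant in 8% of trials at a loading of 0.3 on severity (share 9%), 26% at 0.5 (25%) and 81% at 0.7 (49%). The pattern is the same.

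**Alternatives under the same models.** Correlating within-block change with change, or the tDCS-minus-sham difference in change for both measures, gives a mean r of about 0 and 4% to 6% significant in every setting. For the within-block version this follows from the model, because fixed severity cancels. If rates of decline differ between people and shared decline explained 30% of the variance of both changes, the arithmetic above applies again: r of about 0.30 and about 37% significant at n = 30. A person's own steady decline cancels in the tDCS-minus-sham difference when the two blocks are equally long.

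**The case against.** The strongest reply is that the gap is narrower than it looks. Hypotheses 2a and 2b do contrast each metabolite between tDCS and sham, and do tie it to language gain at the stimulated site. Because the correlation is also evaluated before treatment, one driven by severity should already be visible there. No rule says that a significant correlation at one visit will be declared a biomarker.

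The size is also uncertain. The Background compares people with PPA against other groups; it does not show a severity gradient among patients. Section 4 excludes advanced disease, which narrows the range. Accuracy comes from different tasks in different people, some trained to a criterion, which may loosen its tie to severity. At a 10% share the excess over 5% is small.

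Most of this stands and limits the claim. It does not remove it. The link in 2a and 2b is by site, so it does not show whether the people whose metabolite moved are those whose language improved. The pre-treatment correlation is a useful warning, but no comparison between visits is planned. Even with no confounding at all, a correlation of levels does not measure response to tDCS.

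**Conclusion.** The stated person-level analysis does not match the stated objective: it cannot separate response to tDCS from severity, and no other section supplies a within-person or tDCS-minus-sham link. With no tDCS effect, the chance of a significant level correlation at one visit runs from 8% to 83% for severity shares of 10% to 50% at n = 30, and from 6% to 50% at n = 15. These figures rest on assumed shares and an assumed MRS sample.

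Three stronger readings might be inferred and are not supported:

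- That severity will make the correlation positive for both metabolites. It can do so for NAA if NAA tracks severity among patients. For GABA no severity link is stated, and the sign is open.
- That the imaging objective has no valid treatment comparison. The contrasts in 2a and 2b against sham are unaffected.
- That the trial's efficacy conclusion is at risk. Spectroscopy is not among the outcomes in sections 6a and 6b, and the behavioural comparison does not use it.

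This should be fixed; it is not a fatal flaw.

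**What to change.** In Primary Objective 2, with a matching sentence in section 6c, define the biomarker test as a correlation across scanned participants. One variable is the tDCS-minus-sham difference in pre-to-post metabolite change; the other is the tDCS-minus-sham difference in pre-to-post accuracy change over the same blocks. State it separately for NAA and GABA. Include treatment order as a covariate, because a period effect enters these differences with opposite sign in the two sequences.

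Report within-block change-with-change correlations as supportive only, since language therapy is given in both conditions and decline may be shared. Keep the level correlation at baseline, labelled a possible marker of severity.

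No new scans, visits or participants are needed. The cost is precision: differences of changes are noisier than levels, and the MRS subset may be small, so the estimate should be given with its confidence interval. Fixing the form before analysis also avoids a later choice between levels and changes.

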## Primary Objective 3 (molecular mechanisms)

**Part 1:** (A) To determine whether BDNF levels in plasma or saliva are related to language and cognitive decline in PPA, differently in men and women (cross-sectionally, before treatment). (B) To evaluate whether tDCS modulates BDNF levels and language and cognitive performance differently in men and women, relative to baseline (before treatment). We will measure BDNF levels, as well as other synaptic proteins (e.g., NPTX2, NRXN2a, AMPA4), language and cognitive performance, before, immediately after and 6 months post-treatment.

**Part 2:** To measure the correlation between tDCS-induced changes in functional connectivity and BDNF in men and women. We will measure brain and skull anatomical variables from scans, and analyze data from resting state functional magnetic resonance imaging (rsfMRI) before, immediately after, and 6 months post treatment.

*Hypotheses*: (A) tDCS will induce differential functional connectivity (FC) changes in men and women; (B) these FC changes will correlate with changes in BDNF blood levels; (C) and BDNF changes will correlate with changes in therapy outcomes in men and women, after controlling for potential sex-dependent cranial and neuroanatomical differences. (D) Changes will last for up to 6 months.

**Part 3**: To identify whether gene mutations (e.g., val66met) that affect BDNF secretion in men and women with PPA predict tDCS effects on BDNF levels, behavioral outcomes and FC network modulations. We will analyze behavioral tDCS effects (over sham) with regard to the interaction between genetic mutation and sex. We will also test whether known mutations that are responsible for Alzheimer's disease pathology e.g., the APOE4 affect tDCS effects, since this genetic mutation can be isolated with the same genetic sequence procedure (Taqman). We will carry out genetic testing at the beginning of treatment and stratify tDCS groups accordingly.

# 2. **Background** (briefly describe pre-clinical and clinical data, current experience with procedures, drug or device, and any other relevant information to justify the research)

During the past few years, a form of electrical stimulation of the brain, transcranial Direct Current Stimulation (tDCS) has been rediscovered and shown to enhance cortical function (Floel et al., 2008; Fritsch et al., 2010; Wassermann & Grafman, 2005) when anodal current is applied in healthy individuals (Floel et al., 2008; Iyer et al., 2005). So far, tDCS has been mainly used to improve motor and language recovery in post-stroke aphasia (Baker et al., 2010; Fiori et al., 2011, p. 201; Floel et al., 2011; Fridriksson et al., 2011; Hamilton et al., 2011; Monti et al., 2008; Schlaug et al., 2008). A few studies have used tDCS in participants with neurodegenerative diseases such as Alzheimer's Disease (AD) (see(Freitas et al., 2011)for a review) and have shown that it improved recognition memory in those participants (Boggio et al., 2009; Ferrucci et al., 2008; Sparing et al., 2008) especially when applied together with behavioral therapy but long-term effects have not been clearly identified yet. However, we are not aware of any published studies evaluating the effects of brain stimulation using tDCS in participants with PPA. As research advances there is a growing interest in describing the physiological effects of this therapy (Stagg & Nitsche, 2011) as well as the changes it induces to brain activity (Nitsche et al., 2004). A handful of studies have used fMRI to look at the effects of tDCS in the brain either during or after stimulation (Antal et al., 2011; Jang et al., 2009; Kwon et al., 2008; Polania et al., 2011; Stagg et al., 2009). However, all these studies used healthy individuals or rats (Takano et al., 2011). Furthermore, there are only a few treatment studies in PPA (see (Mesulam, 2007), for a discussion) and these studies have focused on the treatment of word retrieval, primarily in semantic dementia, i.e. the semantic variant of PPA (Graham et al., 1999; Henry et al., 2008; Heredia et al., 2009; Jokel et al., 2006, 2010) with encouraging results of language therapy at least for trained items. Similarly, there are also a few studies of behavioral word retrieval treatment in non-fluent/agrammatic PPA (Jokel et al., 2009; Marcotte & Ansaldo, 2010; McNeil et al., 1995; Schneider et al., 2011; Newhart et al., 2009) and only two studies with a spelling intervention one of which is from our lab (Rapp & Glucroft, 2009; Tsapkini & Hillis, 2013). To date we are not aware of any published study that has evaluated the effect of spelling, naming, or repetition therapy combined with tDCS in PPA or MCI participants.

Although we do not know the exact mechanisms by which tDCS works, it has been claimed that the low current applied on the scalp has the potential to alter synaptic excitability at the stimulation area (Nitsche et al., 2004; Stagg & Nitsche, 2011). We therefore hypothesize that effects of generalization to other functions will depend on the area stimulated. In the existing literature effects of tDCS in the areas stimulated have been correlated with the cognitive functions subserved by these areas. Furthermore, it has been shown that stimulation of specific areas affects only functions subserved by these areas but not others; Ferrucci and colleagues (2008) have shown that stimulation of the temporo-parietal junction affected word recognition but not visual attention which was subserved by different areas. There is only one other study that has looked at transfer of treatment effects to other language functions. (Marangolo et al., 2011)) have shown that beneficial effects from syllable production training in combination with stimulation at the left inferior frontal gyrus (IFG) of patients with stroke transferred to other production tasks such as word repetition and reading. In the present study we will test the hypothesis that spelling therapy gains will not only generalize to the spelling of untrained items but also to other language and cognitive functions that are subserved by the stimulated areas. In the same logic, we do not expect generalization to language and cognitive functions that have neural substrates different from the stimulated areas.

We further hypothesize that improvements related to tDCS or sham combined therapy may extend to increases in quality of life as measured by lifestyle activity. Research conducted by [name] lab ([name]) using wearable accelerometers in community-dwelling older adults has demonstrated that low-intensity walking activity related to functional activities of daily living (shopping, vacuuming), were positively associated with several measures of health (self-report and performance-based measures of physical function, quality of life, depressive symptoms) independent of exercise activity (Varma et al., 2013). Low-intensity walking activity is associated with better health. Furthermore, greater daily walking activity was cross-sectionally associated with larger hippocampal volume, an important brain biomarker of memory and risk for dementia (Varma et al., 2015). We hypothesized that the language and other cognitive improvements related to intervention itself (either sham or tDCS) and especially language therapy may further correlate to increases in functional and social activities (e.g. walking to catch a bus, caretaking of grandchildren, and religious activities).

The imaging goal of this study is to develop molecular biomarkers for the effects of intervention using H-MRS. Our aim is to investigate the molecular and cellular mechanisms of tDCS combined with spelling therapy in PPA. In a previous study using spectroscopy, individuals with PPA were found to have a specific neuropeptide signature different from other dementias and healthy controls (Catani et al., 2003), i.e. they had low levels of NAA. In the present study we intend to investigate the modulation of certain

neuropeptides (NAA and GABA) from tDCS. Thus, application of tDCS is expected to increase the levels of NAA and NAA/Cre associated with better performance. Furthermore tDCS is expected to decrease the levels of GABA since anodal tDCS supposedly suppresses the inhibitory system suggesting a locally reduced activity of the GABA-ergic system (Stagg et al., 2011). In the present study we will investigate how tDCS combined with spelling interventions may change the NAA and GABA neurotransmitters' levels.

There is an increasing interest in evaluating the effects of deficits in synaptic transmission and in interventions targeting the molecular mechanisms of synaptic transmission. Recent aphasia studies have shown that the genetic information (specifically BDNF) may influence how tDCS modulates behavior (Fridriksson et al., 2018). This information is important because the BDNF gene may serve as a biomarker for those who have the potential to benefit from tDCS. Furthermore, there is evidence that tDCS modulates (increases) BDNF levels in blood plasma (Marangolo et al., 2014). If this is the case, then BDNF may be a molecular mechanism of tDCS. Given that there is a sex effect of BDNF levels (lower BDNF levels in women)(Chan & Ye, 2017; Dong et al., 2017), we seek to causally test the hypothesis that BDNF is the molecular mechanism of sex differences in frontotemporal dementia (FTD), specifically PPA, because it moderates and modulates tDCS effects. A better understanding of how BDNF moderates and modulates cognitive and language decline as well as tDCS effects in FTD will have a significant impact on the development of effective therapies. If BDNF is a possible endophenotype of cognitive decline in neurodegeneration, and its expression can be modulated by tDCS, this study will provide an exceptional molecular mechanistic target in the attempt to ameliorate cognition and delay the progression of FTD in the framework of personalized medicine. Results will serve as a foundation for multi-center clinical trials on BDNF as a mechanism for reversing neurodegeneration.

The PI and co-investigators have extensive research and clinical experience with all study tasks: behavioral language therapy (including spelling, naming, and repetition therapy; (Hillis, 1989, 1992, 1993) tDCS (e.g. (Yau et al., 2014)) cognitive evaluation of PPA (e.g. (Gorno-Tempini et al., 2011; Sepelyak et al., 2011) and spectroscopy (Gao et al., 2013; Rowland et al., 2012). We have recently completed a study on specifically applying behavioral therapy for the improvement of spelling abilities in both stroke and PPA participants with encouraging preliminary results (Tsapkini & Hillis, 2013). We have documented the course and outcomes of grapheme-to-phoneme conversion treatment in two participants, one with stroke and another with PPA. We showed that the PPA patient could learn the phoneme-grapheme correspondences and showed a dramatic improvement in the phoneme-word associations as well. Other members of the study team have extensive experience with the use of tDCS ([name]), spectroscopy ([name]) and genetic analyses ([name]) and will provide training to the PI and the other members who will be involved in the testing of participants.

